2.12 Publication Plan	
We will publish at least one manuscript describing clinical trial design and results. Our projected target date for publication is six months after closing the trial. We plan to submit the study to the Journal of Vascular Surgery or Clinical Journal of the American Society of Nephrology. We anticipate two abstracts: one each for annual meetings of the Society of Vascular Surgery and American Society of Nephrology

	
See attached.

2.13 Curriculum Vitae	
2.13 Protocol Submission for Investigator-Initiated Studies	
U.S. protocols should be submitted by US investigators directly or through the Global Research Specialist at www.merckiiisp.com
 
Non U.S. protocols should be submitted to the MSD office by the investigators.

## AMENDMENT HISTORY

November 3, 2016:	Final version of SAP. Version 1.0
May 16, 2018:	Vorapaccess SAP revised. Version 2.0 Added a new secondary outcome Added a sentence on the deviation from the planned analysis due to low enrollment and early stopping of trial.
June 11, 2018:	Updated the definition of the secondary outcome ““AV fistula functional or anatomic maturation at 180 days as determined by the PI”

## 1. Introduction

### 1.1. Background

End-stage renal disease affects nearly 500,000 persons in the US and more than 2 million persons worldwide. In the US and most developed countries, hemodialysis is the predominant dialytic modality. While effective at sustaining life for most patients, hemodialysis rarely restores health. Roughly one in five patients on dialysis die each year; patients who survive experience poor functional status, impaired physical and cognitive function and severely impaired health-related quality of life. Moreover, the cost of the ESRD program exceeds \$40B in the US annually (1).

Hemodialysis vascular access is often referred to as the "Achilles Heel" of dialysis care. The Brescia-Cimino (radiocephalic end-to-side) fistula is considered to be the gold standard vascular access (2); upper arm arteriovenous fistulae are often created instead.

Polytetrafluoroethylene (PTFE) grafts are next best, but are frequently complicated by graft "thrombosis," commonly caused not by hematologic abnormalities, but rather by intimal hyperplasia at the venous anastomosis. Unfortunately, the majority of patients have insufficient time to undergo pre-emptive creation of an arteriovenous fistula or graft, and most patients start hemodialysis with either a temporary or "semi-permanent" tunneled catheter, often placed in one of the internal jugular veins.

For patients who do undergo fistula creation, either in advance of (optimally) or after starting hemodialysis, a sizeable fraction of arteriovenous fistulae never matures sufficiently to be usable for hemodialysis. It is common for patients to undergo three or more attempts at fistula creation, extending the time during which they experience a heightened risk of infection and venous stenosis/thrombosis of the internal jugular veins or in some cases other complications including superior vena cava syndrome. Therapeutic agents that could facilitate maturation of arteriovenous fistulae could vastly improve the health and well-being of patients on hemodialysis, and could well result in enhanced survival.

### 1.2. Objectives

1. To determine if vorapaxar safely improves arteriovenous (AV) fistula functional maturation when administered during the maturation process compared with placebo.
2. To determine if vorapaxar safely improves AV fistula patency, allowing for secondary procedures to aid in fistula maturation compared with placebo.
3. To determine if vorapaxar safely facilitates successful cannulation of AV fistulas for hemodialysis compared with placebo.
4. To determine the safety profile of vorapaxar for patients requiring hemodialysis.

### **1.3. Hypotheses**

1. Vorapaxar initiated two days following AV fistula creation will result in improved fistula functional maturation without increased risk of bleeding or other major adverse events.
2. Vorapaxar initiated two days following AV fistula creation will result in improved fistula patency and will increase the utility of secondary procedures to aid in fistula maturation, without increased risk of bleeding or other major adverse events.
3. Vorapaxar initiated two days following AV fistula creation will facilitate successful cannulation of AV fistulas for hemodialysis without increased risk of bleeding or other major adverse events.

## **2. Study Design**

### **2.1. Study Design**

This is a randomized placebo-controlled double-blind pilot trial. Half of enrolled patients will receive the study drug (vorapaxar [Zontivity™] 2.5 mg daily) and half will receive a look-alike placebo.

Patients will be assigned to treatment groups with a 1:1 randomization in blocks of 4 at the conclusion of the AV fistula creation. Patients will be stratified based on fistula location (lower arm versus upper arm). Randomization will be performed after successful creation of an arteriovenous fistula, on the day of surgery. We expect to randomize 50 patients.

The study drug (12-week supply of study drug or placebo) will be dispensed to enrolled patients on the day of surgery. Participants will be instructed to start taking their study medications on Day-two post-surgery.

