2.5 Study Procedures	
Recruitment and Screening: Recruitment will be by invitation and referral from individuals' treating physicians at Stanford and SCVMC. Generally, initial screening will be performed at the time of consultation for dialysis access. Patients who appear to meet the study criteria and express interest in participation will be referred to the study team to be contacted for full screening.
 
Consent: For eligible patients informed consent will be obtained prior to the day of surgery, generally by phone and mail or in person at the preoperative visit.
 
Baseline demographics (preoperative visit, standard of care): The following data, which is collected as standard of care at the preoperative visit, will be utilized for baseline data with patient approval via the consent process:
 
 
• Age, sex, race, ethnicity, past medical history, medications, previous hemodialysis access surgery
 
• Baseline blood pressure in each arm and vascular exam
 
• Baseline vein measurements
 
 
Operative details (standard of care): The following data, which is collected during the AV Fistula Creation Procedure as standard of care, will be utilized for operative data with patient approval via the consent process:
 
 
• Location of anastomosis (lower or upper arm)
 
• Vein used (cephalic or basilic)
 
• Type of fistula (radiocephalic, brachiocephalic, brachiobasilic, other)
 

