
2.5 Study Procedures
	
 
• Quality of artery (normal, moderate calcification, severe calcification)
 
• Palpable thrill through completion (yes or no)
 
• Audible bruit (yes or no)
 
• BARC Bleeding Classification
 
• GUSTO Bleeding Classification
 
 
Randomization: Randomization will be performed after successful creation of an arteriovenous fistula, on the day of surgery.
 
Treatments to be compared: Half of enrolled patients will receive the study drug (vorapaxar [Zontivity™] 2.5 mg daily) and half will receive a look-alike placebo.
 
Study drug: The study drug (12-week supply of study drug or placebo) will be dispensed to enrolled patients on the day of surgery. Participants will be instructed to start taking their study medications on Day-two post-surgery.
 
6-weeks Follow-up Clinic Visit + Ultrasound (standard of care): Patients will return approximately 6 weeks after randomization to the site of their AV fistula creation procedure for a standard-of-care visit where the following data will be collected and provided to the study team:
 
 
• Patency of fistula (yes/no)
 
• Fistula being used for dialysis at least 6 times in 3 weeks (yes/no)
 
• Diameter of fistula by ultrasound
 
• Velocities of fistula by ultrasound
 
• Adverse events
 
• Additional procedures performed to aid in fistula maturation (yes/no) 
 
◦ Type of procedure
 
◦ Successful (yes/no)
 
 
 
• BARC and Gusto Bleeding Classification
 
 
3-month Follow-up Phone Call (study visit): Approximately 3 months after randomization patients will have a study phone call with a member of the research team where the following data will be collected:
 
 
• Patency of fistula (yes/no)
 
• Fistula being used for dialysis at least 6 times in 3 weeks (yes/no)
 
• Adverse events
 
• Additional procedures performed to aid in fistula maturation (yes/no) 
 
◦ Type of procedure
 
◦ Successful (yes/no)
 
 
 
• BARC and Gusto Bleeding Classification
 
 
4-month Follow-up Phone Call (study visit): Approximately 4 months after randomization patients will have a study phone call with a member of the research team where the following data will be collected:
 
 
• Patency of fistula (yes/no)
 
• Fistula being used for dialysis at least 6 times in 3 weeks (yes/no)
 
• Adverse events
 
• Additional procedures performed to aid in fistula maturation (yes/no) 
 
◦ Type of procedure
 
◦ Successful (yes/no)
 
 
 
• BARC and Gusto Bleeding Classification
 
 
6-month Follow-up Clinic Visit + Ultrasound + End of Study (study visit): Patients will have a final study visit at approximately 6 months, at Stanford University Medical Center Vascular Clinic where the following data will be collected:
 
 
• Patency of fistula (yes/no)
 
• Fistula being used for dialysis at least 6 times in 3 weeks (yes/no)
 

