#### **3.4. Statistical Analysis:**

We will derive cumulative incidence plots to depict time to fistula use, stratified by treatment arm and fistula location.

The primary outcome is time to AV fistula maturation, defined as successful cannulation of the AV fistula for six hemodialysis sessions within three weeks.

Subjects who are lost to follow up or who die prior to maturation will be censored at the time of death or last recorded activity.

Our primary analysis will be based on the intention-to-treat principle. To that end, patients will be analyzed according to their randomized treatment assignment, and all patients randomized to treatment assignment will be included in the analysis even if they are lost to follow up or die before the end of their observation period. We will use a log-rank test stratified by location of fistula to assess whether time to maturation of AV fistula differs between treatment arms (vorapaxar versus placebo). The test will be two-sided and conducted at the 0.05 level of significance.

A Cox proportional hazards regression model of treatment arm and other characteristics of interest (if required) will be employed secondarily to estimate an adjusted treatment effect.

Other secondary analyses involve the use of logistic regression techniques to evaluate the effect of treatment on secondary endpoints – use of AV fistula within 180 days, AV fistula patency within 150-180 days and AV fistula functional or anatomic maturation at 180 days as determined by the PI. We will also compare rates of bleeding by treatment arm using t-tests or Wilcoxon rank sum tests as appropriate.

**UPDATED: Based on low enrollment and early termination of the study, the planned analysis as described above will not be conducted. Instead, we will conduct a descriptive analysis only.**

**UPDATED: The secondary outcome “AV fistula functional or anatomic maturation at 180 days as determined by the PI” will be defined using clinically adjudicated after a review of the medical record.**

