#### **4. Statistical conventions**

This section details general conventions to be used for the statistical analyses and presentation of the data. Departures from these general conventions may be given in the specific detailed sections of this analysis plan.

1. SAS Version 9 or R Version 3 will be the statistical software package used for all data analyses.
2. Continuous variables will be presented with mean, standard deviation, median (25th percentile, 75th percentile), minimum and maximum values. Categorical variables will be presented as number of subjects and percentage of number of subjects by levels of the variable.
3. The number and percentage of responses will be presented in the form XX (XX) where the percentage is in the parentheses. Unless otherwise specified, the denominator for percentages will be the number of subjects in a given treatment group within the analysis population of interest. The denominator will be included when it differs from the standard analysis population.

4. All summary tables will include the analysis population sample size (i.e., number of subjects).
5. Change from baseline will be calculated for each period as follows:  
Change from baseline = Post-baseline value – baseline value.
6. Date variables will be formatted as DD-MON-YYYY for presentation. In the case of missing day, month, and/or year information, “NA” will be presented. For example, a date with a missing month and day will be presented as NANAYYYY.
7. Unless otherwise stated, statistical comparisons will be performed using two-sided significance tests. An alpha level of 0.05 will determine significance unless otherwise noted for a specified analysis.
8. When count data are presented, the percentage will be suppressed when the count is zero in order to draw attention to the non-zero counts.
9. Unless specified otherwise, data will be presented by treatment and control subjects.

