## Appendix 1: Tables and figures

Table 1. Demographic characteristics of study population

Characteristics	Treatment		Control	
	Left arm N (%)	Right arm N (%)	Left arm N (%)	Right arm N (%)
Age (years) Mean (SD) Median (IQR)				
Site Stanford University Santa Clara Valley				
Male				
Race White Black Asian American Indian Pacific Islander Other Unknown				
Ethnicity Hispanic Non-Hispanic Unknown				
BMI Mean (SD) Median (IQR)				

Table 2. Baseline clinical characteristics of study population

Characteristics	Treatment		Control	
	Left arm N (%)	Right arm N (%)	Left arm N (%)	Right arm N (%)
Had previous surgery				
Ipsilateral tunnel catheter access				
Permanent ipsilateral AV fistula access				
Permanent ipsilateral AV graft access				
Contralateral tunnel catheter access				
Permanent contralateral AV fistula access				
Permanent contralateral AV graft access				
Other surgery type				
Medical history				
None				
Routinely hypotensive				
Diabetes				
Coronary artery disease				
COPD				
Congestive heart failure				
Peripheral artery disease				
Stroke				
Intracranial hemorrhage				
Hypertension				
Cancer				
Peptic ulcer disease				
Other				
Concomitant Medications				
None				
Daily aspirin				
Statins				
Insulin				
Oral diabetic medications				
Antifungal agents				
ACE inhibitors				
ARBs				
Beta blockers				
Calcium channel blockers				
Other antihypertensive				
Diuretics				
Antiarrhythmics				
Other medications				

Table 3. Efficacy and safety outcomes

	Treatment		Control		Hazard ratio (95% CI)
	Left arm N (%)	Right arm N (%)	Left arm N (%)	Right arm N (%)	
Efficacy outcomes					
Time to fistula maturation (days) Mean (SD) Median (IQR)					
AV fistula use within 180 days of surgery					
AV fistula patency at 150- 180 days, with at least 50% increase in vein diameter by ultrasound compared with preoperative vein diameter measurement					
Safety outcomes					Odds ratio (95% CI)
BARC bleeding Type 0 Type 1 Type 2 Type 3a Type 3b Type 3c Type 4 Type 5					
GUSTO bleeding Mild Moderate Severe					

Table 4. Adverse events and other outcomes

	Treatment		Control		Odds ratio (95% CI)
	Left arm N (%)	Right arm N (%)	Left arm N (%)	Right arm N (%)	
Serious adverse events					
Unexpected adverse events					
Other adverse events					
None					
Anemia					
Depression					
Rash					
Iron deficiency					
Retinopathy					
Retinal disorder					
Diplopia/oculomotor disturbances					
Other					
Other outcomes					

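### SAP Tables 1-4 split each treatment group by left and right arm instead of the lower/upper stratification factor, and have no overall column per randomised group

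*SAP*

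**What the plan says.** The text of the two documents is consistent about the factor. SAP 2.1, in line with Protocol 2.3, says of the randomisation: "Patients will be stratified based on fistula location (lower arm versus upper arm"). Protocol 2.5 puts the same variable first among the operative data: "Location of anastomosis (lower or upper arm"). SAP 3.4 uses it twice, for the primary test ("We will use a log-rank test stratified by location of fistula") and for the plots ("We will derive cumulative incidence plots to depict time to fistula use, stratified by treatment arm and fistula location"). Figure 1 in SAP Appendix 1 is likewise a Kaplan-Meier plot by treatment and fistula location.

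The tables in the same appendix differ. Under both Treatment and Control, each of Tables 1-4 has two sub-columns, one headed left arm and one headed right arm. There is no third sub-column for the whole group.

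Two other parts of the SAP bear on this. Convention 9 in SAP 4 makes presentation by treatment and control the default, and convention 3 takes the treatment group as the default denominator for percentages. The preamble to that section leaves room for exceptions: "Departures from these general conventions may be given in the specific detailed sections of this analysis plan". The update in SAP 3.4, made after low enrolment and early termination, withdraws the planned analysis: "Instead, we will conduct a descriptive analysis only".

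**The concern.** In a descriptive report the tables carry most of the result. If Appendix 1 is followed as drawn, every baseline, efficacy and safety summary is given by side of body within treatment group. No such summary is given for a randomised group as a whole, and none by the factor on which randomisation was stratified. The row for the primary outcome, "Time to fistula maturation (days) Mean (SD) Median (IQR"), is laid out the same way.

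A reader of the tables could not see how many lower-arm and upper-arm fistulas each group had, and would have to add sub-columns together to compare vorapaxar with placebo. An already small trial would also be divided by a factor for which the plan gives no reason.

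**Working it through.** The plan states no figure to reproduce here, so the check is a comparison of the text with the tables, plus a few counts.

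**Where each factor appears**

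| Place | Lower/upper location | Left/right side |
|---|---|---|
| Randomisation (Protocol 2.3, SAP 2.1) | stratum | no |
| Operative data (Protocol 2.5) | first item | not listed |
| Log-rank test (Protocol 2.7, SAP 3.4) | stratum | no |
| Cumulative incidence plots (Protocol 2.7, SAP 3.4) | split | no |
| Figure 1 (SAP Appendix 1) | split | no |
| Tables 1-4, columns | no | yes, 4 of 4 |
| Tables 1-4, rows | no | only implied, in Table 2 |

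**Could location be read from another row?** Fistula type (radiocephalic, brachiocephalic and so on) would allow it, but no table includes it. Lower/upper location is therefore absent from 4 of 4 tables.

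**Is side recorded?** The operative list in Protocol 2.5 has 8 items: location, vein used, fistula type, artery quality ("Quality of artery (normal, moderate calcification, severe calcification")), thrill, bruit, BARC and GUSTO. None is side. The preoperative list mentions blood pressure in each arm. Table 2 has ipsilateral and contralateral prior-access rows, which cannot be filled in without knowing the side of the fistula. So side is implied as background information, but nowhere as a factor of analysis.

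**Is there a group total?** The count of overall descriptive columns is 0 of 4. Tables 3 and 4 have one effect column (hazard ratio or odds ratio) that is not split by side, but this is a contrast and does not describe either group.

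**Is this an artefact of the text extraction?** That is unlikely. The same two heads recur under both groups in all four tables, 2 × 2 × 4 = 16 heads. A broken table can displace words but would not replace lower/upper with left/right each time. Nor can arm here mean treatment arm, since the heads sit beneath Treatment and Control.

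**How much imbalance on location could go unseen?** A 1:1 block of 4 holds two patients of each treatment, so the running difference within a block never exceeds 2. If blocks run separately within each location stratum, which the documents imply but do not spell out, the treatment difference is at most 2 patients per stratum.

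**The case against.** The strongest reply is that this is a labelling slip in an appendix. All the operative text uses lower/upper, and no randomisation, test or figure depends on the table heads. A slip is plausible, but the documents do not say so. Whether slip or intention, the heads as they stand do not match the plan.

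Second, the conventions allow departures, and the tables may themselves be one. This stands: a reader might infer a breach of convention 9, but the wording does not support that. What remains is that the default is set aside without a stated reason.

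Third, nothing says the tables will be used unchanged. They still carry hazard-ratio and odds-ratio columns after the move to description only, and Table 3 lacks the secondary outcome added in 2018, so they need redrawing anyway. This too stands and makes the consequence conditional. But Appendix 1 is the only table layout the SAP gives, and the redrawing is the occasion to correct it.

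Fourth, little information is lost for good. Figure 1 and the cumulative incidence plots show maturation or use by location. Counts can be summed, and means and SDs combined. Pooled medians and IQRs of age, BMI and time to maturation cannot be rebuilt from the printed tables, but the trial team holds patient-level data in REDCap and can compute them. The plan also never undertook to show bleeding, adverse events or secondary outcomes by location, so their absence in that form is not a fault.

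**Conclusion.** The point holds as a minor inconsistency in the reporting tables. All four divide the randomised groups by a factor that is not used for stratification, modelling or subgroups; none shows lower/upper location; none has a column per randomised group. Its practical weight comes from the change to a descriptive analysis, and it rests on the assumption that the Appendix 1 layout would be followed as drawn.

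Two stronger readings should be avoided. A reader might infer that randomisation or the planned log-rank test used the wrong stratum; the text of both documents is consistent on lower/upper location, so neither is affected, and nor is Figure 1. A reader might also infer that side of body has no place in the plan at all; the prior-access rows of Table 2 imply it, so the claim is limited to its use as a factor of analysis. The balance argument is modest, given the cap of 2 per stratum. The final enrolment is not stated in the documents, so the size of the actual sub-columns cannot be given.

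**What to change.** In Tables 1-4, replace the left/right sub-columns with one overall column for Treatment and one for Control, in line with conventions 3 and 9. Add lower/upper fistula location as a baseline row in Table 2, and break down the time-to-maturation row of Table 3 by it.

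This is preferable to lower/upper sub-columns throughout. Even at the planned 50 patients, four sub-columns would average 50 / 4 = 12.5 patients against 50 / 2 = 25 per group, and enrolment fell short of that. Bleeding and adverse events by location are optional. If side of body is of interest, one row in Table 2 is enough. Enter the change in the SAP's amendment history.

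The cost is limited to editing the shells: location is recorded at surgery and was needed to randomise. Sample size, power and significance level do not change.
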